3.0 Inclusion and Exclusion Criteria

3.1 Screening for eligibility

Initial eligibility criteria will be assessed by telephone. Potential participants who remain eligible after the telephone screening will be scheduled for a baseline visit, where they will undergo additional testing to determine their eligibility for randomization.

3.2 Inclusion and Exclusion Criteria.

Inclusion Criteria. All participants will have PAD. PAD will be defined as follows. First, an ABI ≤ 0.90 at the baseline study visit is an inclusion criterion for PAD. ABI ≤ 0.90 is a well-accepted standard for defining PAD (61-64). Second, potential participants who have an ABI > 0.90 but ≤ 1.00 and experience a 20% or higher drop in ABI after heel-rise exercise will be eligible. Third, potential participants with an ABI > 0.90 who have vascular lab evidence of PAD or angiographic evidence of PAD will be eligible. Finally, potential participants with a history of lower extremity revascularization who do not meet the criterion above and have an ABI > 0.90 with a 20% or higher drop in ABI after heel-rise exercise will be eligible.

Exclusion Criteria.

1. Above or below knee amputation, critical limb ischemia, wheelchair confinement, inability to walk without a walker, or current foot ulcer. These are exclusion criteria because they prevent full participation in the intervention or imply an underlying impairment that is too severe to be improved with trial interventions.
2. Walking is limited by a condition other than PAD. This is an exclusion because the intervention is designed to improve PAD-related walking impairment.
3. > Class II NYHA heart failure or angina, increase in angina, angina at rest, or abnormal baseline treadmill stress test. This is an

PROTOCOL TITLE: Telmisartan Plus Exercise to Improve Functioning in PAD: The TELEX Trial

exclusion because exercise may not be safe for these individuals. Potential participants may become eligible following an abnormal baseline treadmill stress test if they have evidence of an absence of coronary ischemia based on testing with their own physician.

4. Currently taking an angiotensin receptor blocker or an ACE inhibitor or use of these medications in the past three months. This is an exclusion because these individuals are already receiving a major component of the trial intervention.

5. Currently taking aliskiren (Tekturna). This is an exclusion because telmisartan may not be safe to take concurrently with aliskiren.

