9.0 Procedures Involved

[figure not shown]
9.1 Study design.

STUDY OVERVIEW. We will randomize a minimum of 112 and up to 240 participants with PAD to one of four parallel study arms: Group A: telmisartan + supervised exercise; Group B: telmisartan + a "no exercise"

PROTOCOL TITLE: Telmisartan Plus Exercise to Improve Functioning in PAD: The TELEX Trial

control group; Group C: placebo + supervised exercise; and Group D: placebo + a “no exercise” control group. Participants will undergo baseline testing, a two-week study run-in period, six months of their assigned study group, and six-month follow-up testing (Figure 2).

Figure 2. Overview of the Telmisartan Trial Design.

Telephone screening.

Initial eligibility criteria will be assessed by telephone via a telephone call script. The study will be described to the potential participant and the participant will be asked a series of eligibility questions to determine whether they qualify for a baseline study visit. If they qualify for a baseline visit, we will collect their name, address, telephone number(s), email address, date of birth, gender, race, and ethnicity.

Baseline testing.

Participants will be asked to come to Northwestern Memorial Hospital at baseline for the purposes of providing informed consent. In addition, at the baseline study visits, we will obtain the ankle brachial index (ABI) measurement, to ensure they are eligible for the study. If the participant meets initial eligibility requirements, we may mail a letter to the participant’s physician to notify him or her of their patient’s involvement with the study, unless the participant does not have a physician or requests that we do not notify their physician. We will administer study questionnaires, such as the Walking Impairment Questionnaire and the Short-Form-36 Physical Functioning Score, to obtain information about their medical history. We will perform baseline physical functioning tests including the six-minute walk test, chair stands, balance testing, and the treadmill walking performance test. We will take a blood sample, measure participants’ height and weight, and measure the blood pressure in their arm. In addition, participants will be asked to undergo a calf muscle biopsy at baseline. Participation in the calf muscle biopsy is optional. Participants will be asked to have a physical examination prior to randomization. Baseline study visits will be performed over multiple days.

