Details of baseline visit procedures are described in section 9.2.

Run-in period.

Prior to randomization, all potential participants will be required to successfully complete a two week run-in period, during which they will take

PROTOCOL TITLE: Telmisartan Plus Exercise to Improve Functioning in PAD: The TELEX Trial

20 mgs daily of telmisartan. Participants will also be required to attend one exercise session and one attention control session prior to randomization. Participants will return for a blood pressure check and measurement of potassium and renal function at the end of the run-in period. Participants unable to tolerate telmisartan due to hypotension (i.e. blood pressure \leq 100/50 on telmisartan) or hyperkalemia (potassium level \geq 5.5) or a 30% or greater decline in renal function compared to baseline, measured by eGFR, will be excluded for safety reasons. Participants who fail to take the study medication for 10 or more days in the two-week period (i.e. one pill per day for \geq 10 days out of the 14 day run-in period) will be excluded. Participants who report significant new or increased symptoms of lightheadedness or dizziness during run-in will also be excluded if the symptoms are thought to be related to the study medication. If a participant's blood pressure is less than or equal to 100/50 at the end of the telmisartan run-in period, the blood pressure may be rechecked after 3 to 10 additional days of telmisartan at the discretion of the principal investigator. For instance, if the participant had another medical condition that was thought to be contributing to the low blood pressure after run-in- OR if the blood pressure reading is very discordant from prior readings. If a participant's baseline eGFR substantially differs from their prior recent eGFR values, and the discrepancy in the baseline value, compared to prior recent values, may contribute to a 30% or greater decline in eGFR after run-in, then at the investigator's discretion, the baseline eGFR and run-in may be repeated. This protocol change was approved by the study's Data Safety Monitoring Board during the week of September 14, 2020.

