Calf muscle biopsies. Muscle biopsies will be performed by co-investigator [name] MD, a board-certified neurologist with > 30 years of experience performing muscle biopsies. [name] completed all biopsies for our pilot study. The muscle biopsy will be obtained in the medial head of the gastrocnemius muscle in the leg with lowest ankle brachial index, at the point that is 67% of the distance between the medial malleolus and the medial aspect of the proximal tibia. This site represents greatest calf muscle diameter in >95% of individuals (83). Anesthesia is achieved with subcutaneous lidocaine. Subcutaneous and adipose tissue are dissected until muscle is identified. Approximately 250 mgs of muscle tissue is removed and immediately prepared for freezing at -70 degrees Celsius.

Approximately 100 to 150 mgs of fat may be removed from the subcutaneous fat may be removed from below the fascial line during the muscle biopsy. In patients with more fat tissue, up to approximately 250 mgs of fat will be removed from the subcutaneous fat and from below the fascial line, respectively, at the discretion of the physician performing the muscle biopsy. The fascia and wound are closed with absorbable and subcuticular sutures, respectively. Participants are asked to return for a wound check approximately one week later. At 6-month follow-up, we will repeat the biopsy using identical techniques.

In addition, in a subset of participants, we will obtain a muscle biopsy on both the left and right legs, respectively. These bilateral biopsies could be obtained at baseline, 6-month follow-up, or at both baseline and follow-up. The first biopsy will be performed using our current procedures. The second biopsy will be performed on the opposite leg approximately seven to thirty days later.

The incision at follow-up is made adjacent to the baseline incision. In the open biopsy, muscle tissue is directly visualized, ensuring an optimal muscle sample and providing substantial advantages over blind needle biopsy. Specimens will be stored and analyzed at Northwestern, the University of Florida, and/or the University of Kentucky. Other measures

PROTOCOL TITLE: Telmisartan Plus Exercise to Improve Functioning in PAD: The TELEX Trial

related to skeletal muscle quality and function may also be performed at Northwestern or at laboratories outside of Northwestern.

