Minimizing risk related to telmisartan. Telmisartan is an FDA approved medication. Side effects include sinus discomfort and congestion, back pain, and diarrhea. Other side effects include hypotension, kidney problems, and hyperkalemia. The study drug is in a class of drugs known to lower red blood cell count, potentially causing anemia which may potentially lead to worsening of leg pain, fatigue, and shortness of breath. The drug labeling indicates that a greater than 2 g/dL decrease in hemoglobin was observed in 0.8% telmisartan patients compared with 0.3% placebo patients. However, no patients have needed to stop telmisartan because of anemia. Rarely, serious allergic reactions may happen. Side effects of telmisartan will be carefully monitored. To maximize safety, we will measure blood pressure, liver enzymes, eGFR and potassium level at baseline. Individuals with a baseline blood pressure $< 100/50$, those with baseline hepatic function abnormalities defined as two or more liver function enzyme values greater than 2.5 times the normal value, and those with a baseline potassium > 5.0 will be excluded. Remaining potential participants who successfully complete baseline testing (except the muscle biopsy, which will be performed after successful completion of the run-in) will be asked to complete a two-week run-in, during which they will be asked to take telmisartan 20 mgs daily. Participants will return at the end of the two-week run-in for a repeat blood pressure check and measurement of potassium and eGFR. Individuals with a blood pressure $< 100/50$ or a potassium level ≥ 5.5 at the end of the two-week run-in will be excluded. Individuals with a 30% or greater decline in eGFR following two-week run-in as compared to baseline will also be excluded. If the participant had a baseline eGFR performed by his/her physician within two months of the baseline eGFR for the TELEX trial, the participant's physician's eGFR may be considered the baseline measure, at the study principal investigator's discretion. Finally, after randomization, all participants will be assessed monthly for pill counts, blood pressure monitoring, and administration of an adverse event form and will have their study medication adjusted appropriately. In addition, potassium levels will be measured at month two and at month five of the

PROTOCOL TITLE: Telmisartan Plus Exercise to Improve Functioning in PAD: The TELEX Trial

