Statistical Analyses. Analyses will be performed according to the intention to treat principle. Data will be analyzed according to each participant's originally assigned group, irrespective of whether the participant adheres to the assigned group. For the Primary Aim, we will use analysis of covariance (ANCOVA) to compare changes in six-minute walk performance at 6-month follow-up between Group A+B combined and Group C+D combined, adjusting for study site (Northwestern or Tulane) and randomization to exercise status. For our Secondary Aim 1 and our Secondary Aim 2, we will use two sample two-tailed t-tests to compare changes in six-minute walk at 6-month follow-up between Groups A and B, between Groups A and C, and between Groups B and D, all stratified by study site. For our Secondary Aim 3, we will use ANCOVA to compare changes in maximal treadmill walking distance, the WIQ, and the SF-36 physical functioning score between Groups A + B vs. Groups C + D, adjusting for study site and randomization to exercise. For our Tertiary Specific Aim 1, we will use t-tests to compare maximal treadmill walking distance, the WIQ, and the SF-36 functioning score, between Groups B and D stratified by study site. For our Tertiary Specific Aim 2, we will use t-tests to compare maximal treadmill walking distance, the WIQ, and the SF-36 physical functioning score, between Groups A and B, and between Groups A and C, respectively, also stratified by study site. For our Exploratory Aims, we will use ANCOVA to compare changes in gastrocnemius muscle biopsy measures of each muscle measure between Groups A+B vs. C+D adjusting for study site and randomization to exercise. We will also compare Groups A, B, and C, respectively vs. Group D using two sample t-test stratified by study site. When the distribution of changes in the primary, secondary, and exploratory outcomes of interest is "very non-Gaussian", we will either apply appropriate transformation before conducting t-tests or perform Wilcoxon rank-sum test for the comparisons. Prior to analyses, we will also check the potential imbalance of socio-demographic factors and prognostic factors (such as age, sex, race, baseline outcome measure, ABI, BMI, smoking status, comorbidities, and relevant medication use) between the two groups using t-tests for continuous factors and chi-square test for discrete factors. If there is any indication of major imbalance in these factors or baseline variables are associated with the change in outcome of interest, we will perform ANCOVA to further adjust for the relevant baseline factors as potential confounders, in addition to randomization to exercise status and site, for two-group comparison. Similar analysis will be performed for exploratory aims. In the analysis for the secondary, tertiary and exploratory aims, we will not adjust for multiple testing. However, we will report all the results regardless of their significance to present an overall picture of the treatment effect of

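### The muscle baseline follows the telmisartan run-in while the walking baseline precedes it: the planned between-arm contrasts survive, but muscle change needs relabelling, baseline adjustment and a set exercise-to-biopsy interval

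*Combined protocol and SAP*

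**What the plan says.** **Timing of the biopsy.** Section 9.1 (Baseline testing) lists it with the other baseline tests: "participants will be asked to undergo a calf muscle biopsy at baseline". It does not mention the run-in there. Section 9.3 (Minimizing risk related to telmisartan) describes who goes on to the run-in, "Remaining potential participants who successfully complete baseline testing", and carves out one test: "except the muscle biopsy, which will be performed after successful completion of the run-in". The walk, treadmill and questionnaire baselines therefore come before the run-in and the muscle baseline comes after it.

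**Content of the run-in.** Section 9.1: "Prior to randomization, all potential participants will be required to successfully complete a two week run-in period". It consists of "20 mgs daily of telmisartan. Participants will also be required to attend one exercise session" and one attention-control session. Exclusion 12 in Section 3.2 says the exercise session is on a treadmill and requires pills on at least 10 of the 14 days. Section 9.1 allows 3 to 10 further days of drug before a repeat blood pressure check, or a repeated run-in.

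**Endpoint and analysis.** Section 8.0 defines the exploratory endpoints as changes in biopsy measures, and Table 3 marks them in the same baseline column as walking. In Section 11.2, for the exploratory aims, "we will use ANCOVA to compare changes in gastrocnemius muscle biopsy measures" between Groups A+B and C+D, adjusting for site and exercise assignment. Groups A, B and C are each compared with Group D by site-stratified t-tests. Baseline values enter only if an imbalance or an association with change is found.

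**Exercise.** Groups A and C train three times weekly (Section 9.1). Phosphorylated AMPK is among the markers (Section 9.2). No interval between exercise and biopsy is given for either visit.

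**The concern.** The plan excludes recent users of ARBs or ACE inhibitors (Section 3.2, exclusion 4) with the reason "This is an exclusion because these individuals are already receiving a major component of the trial intervention". Yet each biopsied participant has just been given telmisartan when the muscle baseline is taken. Muscle change and walking change therefore start from different states, and nothing in the plan says so.

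The exploratory aims are meant to identify pathways behind better walking. If muscle responds within the run-in, a real drug effect can show as a fall on placebo and a small rise on telmisartan. A reader of within-arm changes, or of muscle change plotted against walking change, could then draw the wrong conclusion.

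The exercise interval is a separate issue, and it reaches planned contrasts. Section 2.3 E cites mouse work in which exercise raises AMPK. If month-6 biopsies in Groups A and C fall soon after a session, the markers may reflect that session as well as six months of training.

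**Working it through.** **Inputs.** The documents give no biopsy sample size, power, effect size or time course for muscle. I use the following:
- Δ, the six-month drug effect on a muscle marker. For illustration it is 0.566 SD, the detectable difference for the primary outcome in Section 11.2. That statement reproduces: 50 per arm, two-sided 0.05, gives power 0.800 by noncentral t. It concerns walking, so it supplies only a scale.
- f, the share of Δ present at the post-run-in biopsy. This is an assumption, with range 0 to 1.

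**Step 1: mean change.** Let B be the off-drug level. The observed baseline is B + fΔ in every arm. Month 6 is B + Δ on telmisartan and B on placebo.
- Telmisartan change = Δ - fΔ = (1 - f)Δ
- Placebo change = 0 - fΔ = -fΔ
- Difference = (1 - f)Δ + fΔ = Δ, for every f

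| f | telmisartan | placebo | difference |
|---|---|---|---|
| 0 | +0.566 | 0 | 0.566 |
| 0.25 | +0.425 | -0.142 | 0.566 |
| 0.5 | +0.283 | -0.283 | 0.566 |
| 1 | 0 | -0.566 | 0.566 |

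A simulation (400,000 participants per scenario, constant drug effect) gave differences of 0.565 to 0.571 unadjusted and 0.564 to 0.570 with baseline adjustment. Power at 50 per arm stayed at 0.80 to 0.81.

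**Step 2: why the order matters.** Suppose the biopsy came after randomisation, when telmisartan arms had gained a further share g of Δ and placebo arms had lost a share h. The changes would be (1 - f - g)Δ and -(f - h)Δ, and the difference (1 - g - h)Δ. The result in step 1 therefore depends on the biopsy preceding randomisation.

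**Step 3: person-level association.** If everyone responds equally, the run-in subtracts the same constant from each change score and correlations do not move; the simulated pooled values were 0.073 to 0.076 at every f. If response varies between people (SD 0.5, assumed), the correlation of muscle change with walking change falls:

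| f | within telmisartan arms | all arms pooled |
|---|---|---|
| 0 | 0.20 | 0.17 |
| 0.25 | 0.16 | 0.15 |
| 0.5 | 0.11 | 0.12 |
| 1 | 0.00 | 0.07 |

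**Step 4: acute bout.** Let E be the training effect and b what remains of the last session at the month-6 biopsy, with additive effects.
- C versus D: E + b
- A versus D: Δ + E + b
- B versus D: Δ
- A+B versus C+D: [(Δ + E + b) + Δ]/2 - [(E + b) + 0]/2 = Δ

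Only the first two contrasts carry b. The documents give no value for it.

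**Step 5: what baseline adjustment buys.** With equal variances at the two visits and correlation ρ, the error variance is 2σ²(1 - ρ) for change and σ²(1 - ρ²) for ANCOVA, a ratio of (1 + ρ)/2. The simulation assumed a between-person variance of 1 and a visit variance of 0.5, so ρ = 1/1.5 = 0.667 and the ratio is 1.667/2 = 0.83. The true ρ is not in the documents.

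**The case against.** The best defence is that the planned analyses are unharmed. Section 11.2 compares change only between randomised groups, the run-in is common to all arms, and step 1 leaves the difference at Δ. No correlation or mediation analysis of muscle against walking is specified. Biopsy is optional, may not be offered at the added sites (Section 6.0), and serves exploratory aims only. Section 11.2 already permits baseline adjustment when a check calls for it. All of this stands, and it limits the point to labelling, precision and the exercise interval. It does not remove it. The conditional adjustment depends on looking at the data first, and the protection in step 1 rests on an order that the text never states.

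A reader might go further and infer that placebo-arm change is drug withdrawal, that telmisartan-arm change is on-drug to on-drug, and that muscle change cannot be lined up with walking change. The documents do not support this. They give neither f nor the interval from last run-in pill to biopsy. The telmisartan arms go from the run-in dose to one that may be raised, reduced, stopped or replaced by placebo (Section 9.1). At arm level, the muscle and walking contrasts both estimate a randomised six-month difference. Nor can full 14-day exposure be assumed, since 10 pill-days suffice.

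A reader might also worry about bilateral sampling in Section 9.2: "The second biopsy will be performed on the opposite leg approximately seven to thirty days later". Nothing there says the second leg enters the change score, so I draw no conclusion from it.

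The AMPK evidence in Section 2.3 E is from mice and gives no time course after a bout. The size of b is therefore open, but the interval is still uncontrolled.

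**Conclusion.** The point holds for the exploratory muscle aims. The muscle and walking baselines are taken in different states, and the plan does not acknowledge it.
- **Between-arm contrasts:** not biased by the run-in, provided the baseline biopsy precedes randomisation and no run-in effect persists in the placebo arms at month 6.
- **Within-arm muscle change:** shifted by -fΔ in every arm. For Δ = 0.566 SD this is between 0 and -0.566 SD, and f is unknown.
- **Person-level muscle-walking associations:** attenuated only if drug response varies between people. The plan specifies no such analysis, so this is a caution for interpretation.
- **Exercise interval:** A versus D and C versus D can mix an acute bout with training. B versus D carries no training-session residue, and the pooled telmisartan contrast is free of it if effects are additive.

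The primary and secondary outcomes are untouched.

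**What to change.** 1. In Section 11.2, analyse every muscle outcome by ANCOVA with the post-run-in biopsy value and site as prespecified covariates. Include the comparisons of A, B and C with D, and add exercise assignment in the pooled comparison. With that covariate, analysing change or the month-6 value gives the same treatment estimate.
2. In Section 8.0, Table 3 and Section 11.2, call the endpoint change from the post-run-in biopsy, and rest claims on between-arm differences.
3. State that the baseline biopsy precedes randomisation, and reconcile Section 9.1 (Baseline testing) with Section 9.3.
4. In Section 9.2, set one minimum interval between the last exercise bout and the biopsy, the same at both visits. The investigators should choose its length.

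The cost is SAP wording and minor scheduling work. Taking the biopsy before the run-in would align the two baselines, but some people would be biopsied who then fail the run-in. That is a trade-off for the investigators, and the planned contrasts do not require it.
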